7.4.2 SERIOUS ADVERSE EVENT REPORTING

The PI, Sub-I, or research nurse coordinator is responsible for recording and reporting SAEs. The following procedure will be followed for reporting and handling SAEs:

The research nurse coordinator will notify the PI or Sub-I immediately on becoming aware of a potential SAE. After business hours, PI or Sub-I can be reached via pager system at [contact] or [contact]. PI or Sub-I is responsible for assessing each event and will determine if the event meets the criteria for an SAE, the SAE severity, its relationship to the study intervention, and if the event was expected. PI or Sub-I assessment will be communicated to the research nurse coordinator who will record the event on the SAE form. Because each federal and local have their own reporting requirements, SAE reports will be filed in accordance with their respective time requirements.

The SAE will be followed until satisfactory resolution or the PI or Sub-I believe the situation is stable or chronic. Any other supporting documents or follow-up reports will be completed and submitted if warranted. The IRB will be notified of any unexpected fatal or life-threatening SAE within 7 calendar days of receipt notification.

7.4.3 UNANTICIPATED PROBLEM REPORTING

Incidents or events that meet the OHRP criteria for UPs require the creation and completion of an UP report form. PI or designee will be responsible for reporting UPs to the IRB. The UP report will include the following information:

- Protocol identifying information: protocol title and number, PI's name, and the IRB project number.
- A detailed description of the event, incident, experience, or outcome.
- An explanation of the basis for determining that the event, incident, experience, or outcome represents an UP.
- A description of any changes to the protocol or other corrective actions that have been taken or are proposed in response to the UP.

To satisfy the requirement for prompt reporting, UPs will be reported using the following timeline:

- All UPs, whether they are SAEs or not, will be reported to the IRB within the institution's specific time frame of the PI or Sub-I becoming aware of the event.

7.4.4 EVENTS OF SPECIAL INTEREST

Not applicable.

7.4.5 REPORTING OF PREGNANCY

Pregnant females are excluded from the study. Women of child bearing age will undergo pregnancy testing on entry and will be asked to be on at least one form of contraception. Pregnancy testing will be done at each study visit if there is any suspicion of possible pregnancy. Study medications will be terminated immediately upon the discovery of pregnancy.

7.5 STUDY HALTING RULES

A halt to the study will be considered by the study team if new information becomes available or adverse events connected with the study suggest that continuation of the study is not in the best interest of the participants. Should this happen, the PI or Sub-I will inform the IRB within 24 hours of the decision and will provide the IRB with written documentation detailing the circumstances leading to this decision. The PI or Sub-I will notify all regulatory bodies, ClinicalTrials.gov, and the FDA of the disposition of the study.

7.6 SAFETY OVERSIGHT

7.6.1 ROUTINE SAFETY OVERSIGHT

Safety oversight will be under the direction of the PI from first participant screening through study completion. Safety labs are done at entry (to establish baseline) and at each subsequent study visit at day 4, 10 and 21. The results of these safety labs are reviewed by the research nurse within 24 hrs of the blood draw and any concerning abnormality reviewed with the research physician. The status of all participants on study are reviewed at weekly staff meetings.

7.6.2 DATA SAFETY MONITORING BOARD (DSMB)

As this is a small single-site pilot study and not a phase III study, a DSMB will not be convened for this study. It is anticipated that safety of the participants can be ensured by close monitoring and review of all participants on study at weekly staff meetings.

8 CLINICAL MONITORING

Quality assurance monitoring will be performed by the Unit Coordinator of the Hawaii Center for AIDS to ensure the safety of the participants, to ensure that the rights and well-being of human subjects are being protected, that the reported trial data are accurate, complete, and verifiable, and that the conduct of the trial is in compliance with the currently approved protocol/amendment(s), with GCP, and with applicable regulatory requirement(s).

Careful attention will be paid to GCP, applicable regulatory requirements, and the need to ensure the safety of the participants. All efforts will be expended to make sure that procedures are followed and that appropriate documentation is in place should site monitoring be requested by the IRB or other regulatory bodies.

9 STATISTICAL CONSIDERATIONS

9.1 STATISTICAL HYPOTHESES

Primary hypothesis Maximum severity of disease, as assessed by the modified 7-point Clinical Status ordinal scale, will be less in the telmisartan arm compared to the placebo arm

Secondary hypotheses

- Telmisartan will be safe and well tolerated in symptomatic patients with COVID-19 over the 21 day study period
- Telmisartan will increase Ang(1-9), AngII and Ang(1-7); Elevated levels of these peptides in relation to angiotensin peptide receptors such as MasR, AT1R and AT2R expression will be important predictors of improved clinical outcomes
- Differences in biomarker levels will be seen between the 2 arms; Certain baseline values may predict clinical outcomes

Exploratory hypothesis:

- Loss of viral detectability will be faster in the telmisartan arm compared to the placebo arm

9.2 ANALYSIS DATASETS

The analysis dataset will include all subjects enrolled into the study with data from entry to the final day 21 study visit.

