4.1.1 PRIMARY ENDPOINT

The primary endpoint is the maximum clinical severity of disease for each participant as assessed on a 7-point **Clinical Status** ordinal scale adapted from the WHO MASTER PROTOCOL for the Treatment of COVID-19 in Hospitalized Patients. The WHO 7-point scale was modified by adding sub-categories for the categories of 'Not hospitalized, limitation on activities' (based on scoring on a **Symptom Scale** to be filled out by participants daily, as explained below), as well as for the 'Hospitalized, requiring supplemental oxygen' and 'Hospitalized, on non-invasive ventilation or high flow oxygen devices' categories. For non-hospitalized participants, the maximum clinical severity recorded for any day \geq day 3 of study will be used. For participants who become hospitalized, the maximum clinical severity prior to discharge will be used.

Clinical Status Classification	Score
Not hospitalized, no limitations on activities	1.0
Not hospitalized, limitation on activities as assessed by the Symptom Scale below	
(a) \leq 3 points	2.0
(b) 4-6 points	2.25
(c) 7-9 points	2.5
(d) 10-12 points	2.75
Hospitalized, not requiring supplemental oxygen;	3.0
Hospitalized, requiring supplemental oxygen:	
(a) Requiring supplemental oxygen at < 6 L/min	4.0
(b) Requiring supplemental oxygen at ≥ 6 L/min	4.5
Hospitalized, on non-invasive ventilation or high flow oxygen devices	
(a) Non rebreather mask	5.0
(b) Noninvasive ventilation (NIV), high flow O ₂ devices	5.5
Hospitalized, on invasive mechanical ventilation or ECMO	6.0
Death	7.0

'**Symptom Scale**' to be used for sub-classification of the 'Not hospitalized, limitation on activities' category on the modified WHO 7-point ordinal scale is as shown below. The participant will be asked to daily grade each symptom by severity to obtain a total score. For example, the assessment of grade 2 fever (2 points), grade 1 breathing (1 point) and grade 3 fatigue (3 points) will result in a total score on the symptom scale of 6 for that day. Referring back to the **Clinical Status** classification above, the clinical status on the 7 point ordinal scale would be 'not hospitalized, limitation on activities (b) 4-6 points' for a clinical status score for the participant on that day of 2.25.

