9.3 DESCRIPTION OF STATISTICAL METHODS

9.3.1 GENERAL APPROACH

This is a prospective, randomized, double-blind 3-week study of telmisartan vs placebo in symptomatic individuals diagnosed with COVID-19 disease. Subjects will be randomized 1:1 to receive telmisartan vs placebo for 3 weeks (21 days). A block randomization will be applied to ensure the balance of participant numbers and baseline severity between treatments.

The baseline characteristics of participants will be summarized by descriptive statistics and compared between the two groups to check any imbalance. The primary efficacy endpoint for the study is an ordinal outcome corresponding to the maximum clinical status of the study subject. The proportional odds model and logistic regression techniques will be applied to compare the ordinal outcome between treatments, based on odds ratios. There are several secondary efficacy endpoints defined for the study. For those measures, averages and rates will be compared between groups, appropriately. Longitudinal mixed-effects models will be utilized to handle longitudinal outcome measures observed at days 1, 4, 10, and 21. The covariate use in regression models will be limited due to the relatively small sample size. Tests of normality will be performed on continuous data and transformation applied where applicable. Type-I error for hypothesis tests will be fixed at 5% nominal level. All efficacy and safety estimates (e.g.

average and proportions) will be provided with 95% confidence intervals (95% CI). The multiplicity error in exploratory analyses will be corrected via the false discovery rate. All efforts will be taken to minimize loss-to-follow-up. However, small amounts of missing data may occur. In such cases, participants without final outcome data will be excluded from the analysis. Sensitivity analysis with multiple imputations will be performed for confirming results. Statistical analyses will be performed using the R software 3.5.1 version.

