9.5 MEASURES TO MINIMIZE BIAS

9.5.1 ENROLLMENT/ RANDOMIZATION/ MASKING PROCEDURES

After signing the Informed Consent Form (ICF), the subject is assigned a unique patient identifier number (PID). At the time of enrollment (randomization), the subject is assigned a unique subject identifier number (SID). PIDs and SIDs are not re-assigned. Screening Numbers and Subject Numbers are not re-assigned. Subjects are randomly allocated (1:1) to active medication (telmisartan) or placebo.

Randomization may occur after verbal informed consent has been obtained from the subject or representative, and subject eligibility has been confirmed. A study enrollment form will be sent to the research pharmacist to initiate the randomization process and assign the treatment to the participant. The research pharmacist will obtain the randomized treatment allocation from a computer-generated randomized treatment list for the subject and the pharmacist or designated staff will prepare the study medication. The study medication will not be provided to the participant however until a written informed consent is obtained. The site research staff and investigators (with the exception of the research pharmacist) will not have access to the treatment assignments and investigational drug products are over-encapsulated to blind the study drugs.

Since the research pharmacist is unblinded in order to provide the assigned treatment, the research pharmacist will not be involved with the assessment of outcomes or data capture except as necessary to manage drug distribution, control and accountability.

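### Sections 9.2 and 9.3.1 can be read as a day-21-completer rule, which would drop randomised participants who already have a primary endpoint score

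*Combined protocol and SAP*

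**What the plan says.** - **Analysis set (9.2).** The whole definition is "The analysis dataset will include all subjects enrolled into the study with data from entry to the final day 21 study visit". No intention-to-treat, modified or per-protocol set is defined anywhere.
- **Missing data (9.3.1).** After allowing for small amounts of missing data from loss to follow-up, the plan states that "participants without final outcome data will be excluded from the analysis". The term final outcome data appears only there. The section continues: "Sensitivity analysis with multiple imputations will be performed for confirming results". It gives no imputation model or population.
- **Primary endpoint.** Section 9.3.1 says: "The primary efficacy endpoint for the study is an ordinal outcome corresponding to the maximum clinical status of the study subject". Section 4.1.1 builds the score as follows: "For non-hospitalized participants, the maximum clinical severity recorded for any day" from day 3 onward; "For participants who become hospitalized, the maximum clinical severity prior to discharge will be used"; death scores 7.0. No day 21 value and no minimum number of diary days is required.
- **Enrolment (9.5.1).** "At the time of enrollment (randomization), the subject is assigned a unique subject identifier number (SID"), so enrolled means randomised. Also, "Randomization may occur after verbal informed consent has been obtained from the subject or representative"; study drug is withheld until written consent.
- **Follow-up.** Logs are photographed at the day 4, 10 and 21 visits (6.4.7, 6.4.8). A withdrawal needs no discontinuation visit (5.4.2). No study procedures take place in hospital (6.4.10).

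**The concern.** Two readings of 9.2 are open. As a data window, it takes everyone randomised and uses whatever was recorded up to day 21. As a completer rule, it takes only those with data through the day 21 visit, and 9.3.1 excludes the rest.

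On the completer reading, the analysis would discard people whose primary score already exists:

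- participants who die before day 21;
- participants in hospital on day 21;
- withdrawals whose log was captured at the day 4 or day 10 visit;
- participants who stop study drug because they cannot make scheduled visits, which 5.4.1 lists as a reason for stopping.

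The first two groups would leave because of the outcome being measured. Two statisticians could follow the same text and analyse different people, and nothing prevents that choice from being made after unblinding.

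**Working it through.** **1. Inputs.** Section 9.4: 20 per arm; placebo probabilities {0.40, 0.40, 0.05, 0.04, 0.04, 0.04, 0.03}; odds ratio 5.0; 5% type I error; about 80% power. Section 9.3.2: one-sided test. The printed telmisartan vector has six entries for seven categories and sums to 0.99, so the telmisartan vector is derived from placebo by multiplying the cumulative odds by 5. For category 1: 0.40/0.60 × 5 = 3.333, and 3.333/4.333 = 0.769. The full vector is {0.769, 0.183, 0.014, 0.010, 0.009, 0.009, 0.006}.

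**2. The plan's own figure.** Whitehead's formula: power = Φ(ln OR × √V − z), with V = n²·2n / [3(2n+1)²] × (1 − Σp̄³), where p̄ is the mean of the two vectors.

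- Σp̄³ = 0.225
- V = 16000/5043 × 0.775 = 2.46
- ln 5 × √2.46 = 1.609 × 1.568 = 2.524
- Power = Φ(2.524 − 1.645) = 81.0%

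Simulating the proportional-odds score test (tie-corrected rank-sum) gives 80.2%, with type I error 5.0%. The stated 80% therefore reproduces, as a one-sided test with all 40 analysed. All figures below come from the same simulation.

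**3. Completer reading.** Expected deaths are 20 × 0.03 = 0.6 on placebo and 20 × 0.006 ≈ 0.12 on telmisartan. Expected participants in categories 3-7 are 4.0 and 0.95.

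| Who leaves | Power |
|---|---|
| Nobody | 80% |
| Deaths only | 78% |
| Deaths and 25% of categories 3-6 | 75% |
| Deaths and 50% of categories 3-6 | 71% |
| All of categories 3-7 | 62% |

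The last row is an upper bound on the damage, because patients discharged before day 21 are asked to return for visits. The 25% and 50% shares are assumptions.

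**4. Other withdrawals, equal random loss.** The documents give no withdrawal rate, so the rates are assumptions. A participant kept with partial follow-up has a truncated maximum. Two versions bracket the result: every symptomatic withdrawal was already recorded at status 2 (later hospitalisation missed), or every withdrawal with worst status 2 or above was recorded one category too low.

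| Loss per arm | Dropped | Kept, one category low | Kept at min(true, 2) |
|---|---|---|---|
| 10% | 76% | 77% | 80% |
| 20% | 72% | 73% | 80% |

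**5. Type I error.** No true effect, loss only among worst status 2 or above, telmisartan versus placebo:

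| Loss | Dropped | Kept at min(true, 2) | Kept, one category low |
|---|---|---|---|
| Equal (10% or 20%) | 5.0% | 5.0% | 5.0% |
| 10% v 5% | 5.8% | 5.4% | 6.1% |
| 15% v 10% | 5.9% | 5.4% | 6.2% |
| 20% v 10% | 7.0% | 5.8% | 7.6% |
| 20% v 0% | 9.1% | 6.6% | 11.1% |

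In the reverse direction, 5% v 10% dropped gives 4.3%. Keeping truncated scores can therefore be better or slightly worse than dropping them. The plan gives no probabilities for sub-levels 2.0 to 2.75, so these tables do not model them.

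**The case against.** **The data-window reading is natural.** Section 9.2 begins from all enrolled subjects, 9.5.1 equates enrolment with randomisation, and 9.3.1 names the maximum clinical status as the primary outcome, so final outcome data could simply mean that score. On this reading nothing conflicts. This stands as a possible reading, and a reader who infers that the plan certainly excludes deaths goes further than the text. But 9.2 speaks of the final day 21 visit, 9.3.1 speaks of final outcome data in the context of loss to follow-up, and neither refers to 4.1.1. Nothing rules out the completer reading, and even the data-window reading lacks an as-randomised statement and a rule for partial follow-up.

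**Other analyses already cover it.** Multiple imputation is planned, and the mixed model in 9.3.2 can use visits before dropout. The first is a sensitivity analysis and the second is additional to the primary analysis. Neither says who is in the primary set.

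**Keeping truncated maxima may gain little.** This stands. It is tempting to infer that the fix restores 80% power, but that holds only if symptomatic withdrawals were already recorded at status 2. Symptoms required at entry do not secure this, because scoring of non-hospitalised participants starts at day 3 and the plan itself puts 40% of placebo participants in category 1. Sub-levels matter too. With the 0.40 in category 2 split equally over four sub-levels (an assumption) and all lost symptomatic participants recorded at 2.0, type I error when kept is 5.9/5.9/7.0/9.4% for the four unequal cases, no better than dropping.

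**Unequal loss is speculative.** This also stands. The trial is double-blind, and section 2.2.1 reports adverse-event incidence similar to placebo and infrequent discontinuation, though in a different population.

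**Conclusion.** The point holds as an exclusion rule that the text permits and that conflicts with the endpoint. Followed literally, 9.2 and 9.3.1 can remove randomised participants who have a valid 4.1.1 score, and the clearest cases, deaths and hospital stays at day 21, leave for reasons tied to outcome. On the plan's own vectors the cost is about 2 power points if only deaths leave and about 5 if a quarter of categories 3-6 also leave; the drop to 62% is a bound, not an expectation.

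For other withdrawals the gain from keeping the observed maximum is small to moderate: about 1 to 4 points at 10% loss and 1 to 8 at 20%, depending on how far scores are truncated. A reader might infer that the plan inflates type I error. The documents do not support that: it requires unequal loss of symptomatic participants, which no section predicts, and equal loss leaves it at 5%. Nor can it be claimed that the fix always reduces such inflation.

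This should be fixed because one definition settles it cheaply, not because it undermines the trial.

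**What to change.** Reconcile 4.1.1, 9.2 and 9.3.1.

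- **9.2:** *The primary analysis set is all randomised participants who gave written informed consent, analysed in the arm to which they were randomised, whatever their day 21 attendance.* The consent condition is needed because 9.5.1 allows randomisation on verbal consent. With drug withheld until written consent and treatment blinded, it should not select by arm.
- **9.3.1:** define final outcome data as the 4.1.1 score. The primary analysis then keeps deaths at 7.0, hospitalised participants, and withdrawals with at least one recorded status from day 3. Hospital status can come from released records (6.4.6), SAE follow-up to 30 days (7.3) or contact after day 21 (6.4.9).
- **Partial follow-up:** state that the observed maximum is a lower bound. Keep the planned multiple imputation as the sensitivity analysis for partial or absent scores, with no imputed maximum below the observed one. Report a day-21-completer analysis as a further sensitivity analysis.
- **9.3.5:** add to the existing table, by arm, the numbers with partial and with absent scores.

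The cost is a protocol amendment with IRB approval (11.2) and a little analysis work, with no new data collection. Log data are assured only up to the last completed visit, so someone who leaves before day 4 may still have no score. The downside is that truncated maxima may understate severity, which is why the imputation analysis must stay.

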9.3 DESCRIPTION OF STATISTICAL METHODS

9.3.1 GENERAL APPROACH

This is a prospective, randomized, double-blind 3-week study of telmisartan vs placebo in symptomatic individuals diagnosed with COVID-19 disease. Subjects will be randomized 1:1 to receive telmisartan vs placebo for 3 weeks (21 days). A block randomization will be applied to ensure the balance of participant numbers and baseline severity between treatments.

The baseline characteristics of participants will be summarized by descriptive statistics and compared between the two groups to check any imbalance. The primary efficacy endpoint for the study is an ordinal outcome corresponding to the maximum clinical status of the study subject. The proportional odds model and logistic regression techniques will be applied to compare the ordinal outcome between treatments, based on odds ratios. There are several secondary efficacy endpoints defined for the study. For those measures, averages and rates will be compared between groups, appropriately. Longitudinal mixed-effects models will be utilized to handle longitudinal outcome measures observed at days 1, 4, 10, and 21. The covariate use in regression models will be limited due to the relatively small sample size. Tests of normality will be performed on continuous data and transformation applied where applicable. Type-I error for hypothesis tests will be fixed at 5% nominal level. All efficacy and safety estimates (e.g.

average and proportions) will be provided with 95% confidence intervals (95% CI). The multiplicity error in exploratory analyses will be corrected via the false discovery rate. All efforts will be taken to minimize loss-to-follow-up. However, small amounts of missing data may occur. In such cases, participants without final outcome data will be excluded from the analysis. Sensitivity analysis with multiple imputations will be performed for confirming results. Statistical analyses will be performed using the R software 3.5.1 version.

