6.4.5 SCREENING

6.4.5.1 Initial Medical History by Phone Interview

Verbal informed consent and medical history will be obtained by phone or video-conference (selected at caller preference) interview with the potential participant. The interview will record:

- Current Illness: Obtain date of onset of current illness, date of SARS-CoV2 testing and date the positive test was reported back to the participant. Review participant's signs and symptoms associated with the illness with a focus on presence, course, and severity of fever, dyspnea and fatigue. Record grade of fever, dyspnea and fatigue on symptoms scale.
- History of co-morbidities including history of cardiovascular disease including history of hypertension, history of pulmonary diseases; history of pre-diabetes or diabetes, history liver, kidney disease or auto-immune/ immune deficiency diseases and history of alcohol, tobacco, or illicit substance abuse
- Current prescription and over-the-counter medications and medication allergies
- Self-reported weight and height

The potential participant will be asked to bring his or her COVID-19 test result to the person-to-person screening/entry visit. If documentation of the COVID-19 test result is unavailable, the potential participant will be given the option of obtaining it or providing the researchers permission to obtain the test result (this will be done at the Entry visit).

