- The current signs and symptoms will be reviewed and the presence of symptoms sufficient to meet entry requirements will be confirmed. Entry Symptom Scale and Clinical Status to be recorded.
- A photo of the person's COVID-19 test result will be taken. If unavailable and the person opts to have the researchers request it, the person will provide signed permission Consent to Release Information and a photo will be taken of the document. This will permit researchers to obtain the test result document. Also, the person will be asked to sign the Consent to Release in case of hospitalization.

With confirmation of study eligibility:

- Vitals signs will be taken to include temperature, pulse, blood pressure, respiratory rate, and O₂ sat.
- Oro-pharyngeal swab will be obtained
- Blood draw for clinical safety labs and for research assays in quantity as specified in the Schedule of Events.
- The participant will be given a Symptoms log and instructed to daily take and record his/her own blood pressure and temperature. Temperature should also be taken whenever there is tactile fever. The participant will be provided with a digital thermometer and BP monitor as needed and instructed in their use. The participant will be asked to call *immediately* if systolic blood pressure falls below 90 mmHg and to NOT take further study medications unless advised by the study team that it is safe to do so.
- The pharmacist will randomize study participant to telmisartan or placebo; then the study medication will be dispensed to the participant. Participant will be instructed to take first dose as soon as he or she is home.
- Provide the following instructions to participants:
 - Take BP daily at generally the same time of the day and record on Symptoms log. Call research team if SBP is <90 and do not take further study medication unless instructed to do so by the research team.
 - Take temperature whenever a fever is suspected but at least once daily and record
 - Record appropriate fever, dyspnea and fatigue symptoms daily
 - Record the time study medication is taken daily
 - Participants will be advised to take particular effort to remain hydrated, and to be judicious with the use of aspirin or other NSAIDS for fever/symptomatic treatment because it may increase risk for renal problems if excessive amounts are taken with study medication.

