9.4 SAMPLE SIZE

The sample size estimation for the proposed study is not provided considering that this is a pilot study. A total sample of 40 participants will be used in the study (20 per group). The above sample size was determined based on the feasibility assessment. Suppose, in the placebo group, the vector of probabilities for observing the ordinal scale outcomes is {0.40, 0.40, 0.05, 0.04, 0.04, 0.04, 0.03}, respectively for categories 1-7. If we assume the corresponding vector for the experimental treatment group as {0.76, 0.18, 0.02, 0.01, 0.01, 0.01}, that will produce an odds ratio of 5.0 between the two groups. In this scenario, we will have about 80% power to detect a treatment difference using the proportional odds model at 5% type-I error. Also, the selected sample size will allow us to detect a standardized effect size of 0.9 at Cohen's d scale, above 80% power, for a mean comparison between two groups via a two-sample T-test for a Gaussian outcome.

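### Section 9.3.1 says block randomisation will balance baseline severity, but blocking balances only arm numbers, and no severity stratum, cut-point or severity-specific list is specified in 9.5.1

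*Combined protocol and SAP*

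**What the plan says.** Section 9.3.1 (General Approach) gives block randomisation two purposes: "A block randomization will be applied to ensure the balance of participant numbers and baseline severity between treatments".

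Section 9.5.1 (Enrollment/Randomization/Masking Procedures) describes the operation: "The research pharmacist will obtain the randomized treatment allocation from a computer-generated randomized treatment list for the subject". A study enrollment form starts the process, but its fields are not listed. No block size, stratification factor or minimisation rule appears. On timing: "Randomization may occur after verbal informed consent has been obtained from the subject or representative, and subject eligibility has been confirmed".

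Severity is measured early enough to be used. The phone screen (6.4.5.1) instructs staff: "Record grade of fever, dyspnea and fatigue on symptoms scale". The entry visit (6.4.6) adds: "Entry Symptom Scale and Clinical Status to be recorded", listed before the pharmacist randomises.

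On the analysis side, 9.3.6 compares the arms at baseline and 9.3.2 permits adjustment for covariates found to be unbalanced. Section 9.3.1 says that covariate use will be limited because the sample is small. Baseline severity is not named as a covariate in the primary proportional odds model.

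**The concern.** The plan states a property that its named method does not have. Permuted blocks force equal numbers of telmisartan and placebo assignments. They place no constraint on who receives them unless each severity level has its own blocks.

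Severity is the factor for which this matters most. The primary endpoint (4.1.1) is the worst clinical status reached, counted from day 3 for those who stay out of hospital. For those participants it is graded by the same Symptom Scale that is completed at entry. The documents do not quantify how strongly entry severity predicts the endpoint, but it is an obvious prognostic factor. A chance gap can look like a drug effect or hide one, and the report could claim a balance that the method did not provide.

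**Working it through.** **The plan's own figures.** The plan gives no figure for expected imbalance. Its nearest number, about 80% power at an odds ratio of 5.0 (9.4), reproduces as 0.81 with the one-sided 5% test of 9.3.2 (0.71 two-sided). It takes no account of baseline severity.

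**Inputs.** 40 participants, 20 per arm, 1:1 (9.3.1, 9.4). Placebo category probabilities 0.40, 0.40, 0.05, 0.04, 0.04, 0.04, 0.03 (9.4). Assumed, because the documents give no baseline distribution: two severity levels with 30% to 50% in the more severe one, and an odds ratio of 3 to 5 between levels for a worse outcome.

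**Step 1: chance of a gap if the list is unstratified.** Let K of the 40 be severe and k of them fall in the telmisartan arm. With K fixed, k is hypergeometric (40, K, 20) and the gap is |2k − K| participants. If instead each participant's severity is random with probability p, the two arm counts are independent binomial (20, p). A gap of 4 is 4/20 = 20 points and a gap of 6 is 30 points.

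| Severe | Gap ≥ 2, K fixed | Gap ≥ 4, K fixed | Gap ≥ 6, K fixed | Gap ≥ 4, K random | Gap ≥ 6, K random |
|---|---|---|---|---|---|
| 30% | 0.731 | 0.301 | 0.082 | 0.226 | 0.056 |
| 40% | 0.748 | 0.333 | 0.105 | 0.258 | 0.075 |
| 50% | 0.752 | 0.343 | 0.113 | 0.268 | 0.081 |

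So 20 points or more has a chance of 23% to 27% (K random) or 30% to 34% (K fixed). At 20% severe the figures are 16% and 24%.

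**Step 2: does blocking help?** Simulating one list in permuted blocks of 4 (40,000 runs, K fixed) gives 0.303, 0.331 and 0.350 for a gap of 4 or more. These agree with the unblocked values, so blocking on numbers does nothing for severity.

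**Step 3: blocks of 4 within two severity strata.** Each stratum can end in one incomplete block, which at worst splits 2 to 0. The severity gap is therefore at most 2 participants, and a gap of 20 points never occurred in simulation. The arm totals can differ by at most 2 + 2 = 4.

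**Step 4: effect on the estimate with no drug effect.** Take half the participants as severe and 60% scoring 2 or more overall (1 − 0.40 from 9.4). Solve (p0 + p1)/2 = 0.60 for each assumed baseline odds ratio:

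- Odds ratio 3: p0 = 0.472, p1 = 0.728. With 8 severe on telmisartan and 12 on placebo, the arm rates are (8 × 0.728 + 12 × 0.472)/20 = 0.574 and (12 × 0.728 + 8 × 0.472)/20 = 0.626. The apparent odds ratio is (0.626/0.374)/(0.574/0.426) = 1.24.
- Odds ratio 5: p0 = 0.418, p1 = 0.782. The arm rates are 0.564 and 0.636, and the apparent odds ratio is 1.36.
- At 7 v 13, a tail case, the apparent odds ratios are 1.38 and 1.58.

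**Step 5: compared with ordinary noise.** With V = n1·n2·N/(3(N+1)²) × (1 − Σp³) = 16,000/5,043 × (1 − 0.128) = 2.77, the standard error of the log odds ratio is 1/√2.77 = 0.60. With no effect, the estimate ranges over about exp(±1.96 × 0.60), or 0.31 to 3.25.

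**Step 6: the one-sided 5% test, given the gap.** Simulating an unadjusted rank test with no drug effect and the 9.4 placebo probabilities, an 8 v 12 split favouring telmisartan gives a false-positive chance of 9% to 11%. The reverse split gives about 1% to 2%. Averaged over all allocations, the test remains valid.

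**The case against.** A reader might infer that 9.5.1 draws from one unstratified list and so contradicts 9.3.1. The text does not say that. A stratified scheme would also be computer-generated and held by the pharmacist, the enrollment form could carry a severity field, and 9.3.1 can be read as intending blocks within severity. The content of the design schematic is not in the text examined, so a mention of stratification there cannot be ruled out. This objection stands: the fault is a claimed property without a stated mechanism, not a proven contradiction.

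A reader might also infer that a large imbalance is likely. It is not. A gap of 2 or more participants is likely, but a 20-point gap is absent in roughly two-thirds to three-quarters of trials. The shift in the estimate is modest beside a standard error of 0.60 and a planning odds ratio of 5.0. Nor does chance imbalance under valid randomisation inflate type I error on average.

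The plan does have a remedy in 9.3.2, and 9.3.6 looks for imbalance. That remedy is weaker than it appears: it is optional, it depends on seeing the data first, and it competes with the limit on covariates in 9.3.1. Finally, 9.4 assumes that 40% of placebo participants peak at category 1 although all enter with symptoms, so entry severity may carry forward less than one would suppose. That bears on the assumed baseline odds ratio, not on the missing mechanism.

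**Conclusion.** The point holds in this form: block randomisation, followed as written, does not deliver the balance in baseline severity that 9.3.1 claims, and 9.5.1 supplies nothing that would. If the list is unstratified, the chance of a gap of 20 points or more is about 1 in 4 to 1 in 3, against none with blocks of 4 in two severity strata. The range rests on an assumed 30% to 50% in the more severe level. The apparent odds ratios of 1.24 to 1.36 at 8 v 12 rest further on an assumed baseline odds ratio of 3 to 5. The cost is lost precision and a harder reading of one small trial, not an invalid test. The documents do not support saying that the list is known to be unstratified or that serious imbalance is to be expected. The change should still be made: it is cheap and uses data already collected.

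**What to change.** In 9.5.1, specify permuted blocks within two strata of the pre-randomisation Symptom Scale total, for example 0-3 v 4 or more, which is the scale's own boundary between scores 2.0 and 2.25. State whether the phone-screen or the entry assessment defines the stratum, since randomisation may follow verbal consent. Put the stratum on the enrollment form sent to the pharmacist. In 9.3.2, prespecify baseline severity as a covariate in the primary proportional odds model, whatever imbalance is observed.

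If an unstratified list is already in use, remove the reference to baseline severity from the randomisation sentence in 9.3.1 and prespecify the same covariate.

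Cost: one more list, one field on a form, and one degree of freedom in the model. Arm sizes may differ by a few participants, up to 4 with blocks of 4 in two strata. The cut-point is a suggestion; the documents give no baseline distribution from which to choose it.
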